#### **6.2** DATA SHARING PLAN

# 6.2.1 Genomic Data Sharing Plan

Unlinked genomic data will be deposited in public genomic databases such as dbGaP in compliance with the NIH Genomic Data Sharing Policy.

## 6.3 RESPONSE CRITERIA

Response assessments will be performed Day 1 of every cycle during Cycles 1-8 and every third cycle during Cycles 9-20: Cycles 9, 12, 15, 18 and every third cycle during Cycles 21-32: Cycles 21, 24, 27, 30 and end of 32. During the follow-up period, response assessments will be done every 3-6 months, unless being primarily followed at outside facility at which time all effort will be made to receive response data at least yearly.

## 6.3.1 Disease Parameters

- Measurable is defined as any of the following: serum M-protein is ≥ 1 g/dL or "measurable" urine M-spike is ≥ 200 mg/24 hours or serum kappa or lambda FREE light chain of 10 mg/dL along with an abnormal kappa to lambda free light chain ratio.
- The serum free light chain (FLC) assay is of particular use in monitoring response to therapy in patients who have oligo-secretory disease. When using this assay, it is important to note that the FLC levels vary considerably with changes in renal function and do not solely represent monoclonal elevations. Thus, both the level of the involved and the uninvolved FLC isotype (i.e., the involved/uninvolved ratio or involved-uninvolved difference) should be considered in assessing response. The serum FLC assay should be used in assessing response only if the baseline serum and/or urine M proteins are not "measurable" by traditional criteria (serum M protein ≥ 1gm/dL and/or urine M protein ≥ 200 mg/24), and the baseline level of the involved FLC is ≥ 10mg/dL and clonal (abnormal ratio). Patients included on the study on the basis of FLC alone (i.e., no measurable serum/urine) should be the only ones who are evaluated using FLC response criteria. The others should follow usual criteria and ignore FLC results.
- In order to be classified as a hematologic response, confirmation of serum monoclonal protein, serum immunoglobulin free light chain (when primary determinant of response) and urine monoclonal protein (when primary determinant of response) results must be made by verification on two consecutive determinations.
- Caution must be exercised to avoid rating progression or relapse on the basis of variation of radiological technique alone. Compression fracture does not exclude continued

Version Date: 01/01/2024

response and may not indicate progression. When progression is based on skeletal disease alone, it should be discussed with the PI before removing the patient from the study.

- Appearance of monoclonal or oligoclonal bands that are different from original isotype may not be defined as "relapse from CR". Oftentimes, such bands may indicate fluctuations in immunological parameters that are not reflective of MM disease. In these situations, immunofixation and electrophoresis will be interpreted by the clinician before being labeled as "relapse" [47, 48].
- Random urine specimens will be performed day 1 of each cycle (cycles 1-8) and day 1 (or within 7 days prior to day 1) of every third cycle (cycles 9-32). 24-hr UPEPs will be performed to confirm and document "CR" response (once serum and random have become negative for monoclonal protein and immunofixation). In patients whose measurable disease is best determined by measuring Bence Jones protein quantification, a 24 hr UPEP will be performed at baseline, day 1 of each cycle 1-8, and day 1 (or within 7 days prior to day 1) of every third cycle during extension phase I and II. Otherwise, 24-hr UPEP Bence-Jones quantification will be estimated from random UPEP specimens performed at baseline, day 1 of each cycle 1-8, and day 1 (or within 7 days prior to day 1) of every third cycle during extension phase[46].
- As of amendment L (version date 05/17/2018), primary endpoint will be MRD (-) CR rate, therefore per the discretion of the investigator, patients without measurable disease may also be enrolled.
- 6.3.2 Response Criteria adapted from International Myeloma Working Group Criteria for Multiple Myeloma[49] and addition of nCR category[21, 50]
- 6.3.2.1 Evaluation of Response Criteria

# • MRD(-) CR

Complete Response as defined below plus:

Absence of phenotypically aberrant clonal plasma cells by flow cytometry on bone marrow aspirates using the eight-color two-tube approach developed and validated by LP Flow cytometry lab for MRD detection in multiple myeloma with a minimum sensitivity of 1 in 10^5 nucleated cells or higher.

# • Stringent Complete Response (sCR)

Complete Response as defined below plus:

Normal FLC ratio and absence of clonal cells in bone marrow by immunohistochemistry or immunofluorescence (presence/ absence of clonal cells is based on the kappa/ lambda ratio.

# • Complete Response (CR)

Negative immunofixation on the serum and urine and disappearance of any soft tissue plasmacytomas and  $\leq$ 5% plasma cells in bone marrow

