#### 2 ELIGIBILITY ASSESSMENT AND ENROLLMENT

#### 2.1 ELIGIBILITY CRITERIA

- 2.1.1 Inclusion Criteria
- 2.1.1.1 Patients must have histologically or cytologically confirmed Smoldering Multiple Myeloma confirmed by the Principal Investigator in discussion with the Laboratory of Pathology, NCI or the Department of Laboratory Medicine, CC, as needed, and based on the International Myeloma Working Group Criteria[45]:
  - Serum M-protein ≥3 g/dl and/or bone marrow plasma cells ≥10 % and <60%
  - Absence of anemia: Hemoglobin >10 g/dl
  - Absence of renal failure: serum creatinine < 2.0 mg/dL
  - Absence of hypercalcemia: Ca <10.5 mg/dl
  - Absence of lytic bone lesion on X-ray, CT, or PET/CT and not more than 1 lesion on spinal MRI (NOTE: At the discretion of the investigator, PET/CT may replace MRI in patients who have a contraindication to MRI.)
  - Involved/un-involved light chain ratio must be < 100
- 2.1.1.2 Measurable disease within the past 4 weeks defined by any one of the following:
  - Serum monoclonal protein  $\geq 1.0 \text{ g/dl}$
  - Urine monoclonal protein >200 mg/24 hour
  - Serum immunoglobulin free light chain >10 mg/dL AND abnormal kappa/lambda ratio (reference 0.26-1.65)

**NOTE:** As of Amendment L (version date 05/17/2018), the primary endpoint is MRD(-) CR rate; therefore, per the discretion of the Principal Investigator, patients without measurable disease (e.g., M-spike <1) may also be enrolled. This is in line with the most recent IMWG MM response criteria.

- 2.1.1.3 Age ≥18 years. Because no dosing or adverse event data are currently available on the use of carfilzomib in combination with lenalidomide in patients <18 years of age, children are excluded from this study, but may be eligible for future pediatric trials.
- 2.1.1.4 ECOG performance status ≤2 (Karnofsky ≥60%, see APPENDIX A)
- 2.1.1.5 Patients must have normal organ and marrow function as defined below:
  - absolute neutrophil count (ANC) ≥1.0 K/uL
     NOTE: At the discretion of the investigator, patients with an ANC of 0.5 K/uL –
     <1.0 K/uL may also be enrolled if clinically appropriate (e.g., patients with a baseline neutropenia that is chronic and that does not cause complications).

  - platelets >75 K/uL
  - hemoglobin > 8 g/dL (transfusions are permissible)
  - total bilirubin ≤1.5 X institutional upper limit of normal
  - AST(SGOT)/ALT(SGPT) < 3.0 X institutional upper limit of normal (ULN)

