# • Very Good Partial Response (VGPR)

Version Date: 01/01/2024

Serum and urine M-protein detectable by immunofixation but not on electrophoresis or 90% or greater reduction in serum M-protein plus urine M-protein level <100mg per 24h. If the serum and urine M-protein are unmeasurable, a ≥90% decrease in the difference between involved and uninvolved FLC levels is required in place of the M-protein criteria.

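### CR, and so the primary MRD(-) CR, sets no free-light-chain condition for patients whose only measurable disease is FLC, so such a patient can be a primary success while failing VGPR by FLC

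*Combined protocol and SAP*

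**What the plan says.** Section 2.1.1.2 accepts any one of three markers as measurable disease. The third is "Serum immunoglobulin free light chain >10 mg/dL AND abnormal kappa/lambda ratio", with a reference range of 0.26-1.65 for the ratio. A patient can therefore enter with neither serum nor urine M-protein measurable.

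Section 6.3.1 restricts FLC-based assessment to this group: "Patients included on the study on the basis of FLC alone (i.e., no measurable serum/urine) should be the only ones who are evaluated" by FLC criteria, and all others disregard FLC. The same section states that, since Amendment L, the "primary endpoint will be MRD (-) CR rate".

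Section 6.3.2.1 gives an FLC substitute for VGPR: "If the serum and urine M-protein are unmeasurable, a ≥90% decrease in the difference between involved and uninvolved FLC levels is required". PR has a matching 50% rule and PD a matching rule for a rise. The CR definition reads "Negative immunofixation on the serum and urine and disappearance of any soft tissue plasmacytomas", together with at most 5% marrow plasma cells, and does not mention FLC. MRD(-) CR is CR plus "Absence of phenotypically aberrant clonal plasma cells by flow cytometry on bone marrow aspirates", at a minimum sensitivity of 1 in 10^5. Only sCR carries an FLC condition: "Normal FLC ratio and absence of clonal cells in bone marrow by immunohistochemistry or immunofluorescence". MRD(-) CR is built on CR, not on sCR.

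**The concern.** Section 6.3.1 sends FLC-only patients to FLC response criteria, but at the level that defines the primary endpoint there is no such criterion to apply. VGPR requires a 90% fall in the FLC difference; CR and MRD(-) CR, which are meant to be deeper, require no change in FLC. For these patients the marker that made their disease measurable plays no part in the primary endpoint.

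At stake is the MRD(-) CR rate, the one quantity the trial was extended to 50 patients to estimate. A success could be counted in a patient whose only measurable marker is still abnormal. Any effect on the rate runs one way: adding an FLC condition to CR can remove successes but cannot create them.

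**Working it through.** **1. The plan's own figures.** Section 10.1 gives 95% half-widths at n=50. With 1.96 × √(p(1−p)/50):
- p = 0.70: 1.96 × √(0.21/50) = 12.7 points.
- p = 0.85: 1.96 × √(0.1275/50) = 9.9 points.

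Both reproduce. The sample-size arithmetic is not in question.

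**2. The response categories side by side, for a patient with no measurable M-protein (Section 6.3.2.1).**

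| Category | FLC condition |
|---|---|
| MRD(-) CR | none (CR plus negative flow) |
| sCR | normal FLC ratio |
| CR | none |
| VGPR | difference falls by at least 90% |
| PR | difference falls by at least 50% |
| PD | difference rises by at least 25%, and by more than 10 mg/dL |

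Footnote m of Section 3.4, which lets CR be inferred without a repeat marrow in MRD-negative patients on extended dosing, also states no FLC condition.

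**3. A hypothetical FLC-only patient.** At entry, involved FLC is 15 and uninvolved 0.5 mg/dL. The ratio is 15/0.5 = 30, abnormal and below the eligibility limit of 100. On treatment the values are 6 and 0.5.
- Difference at entry: 15 − 0.5 = 14.5. Later: 6 − 0.5 = 5.5.
- Fall: (14.5 − 5.5)/14.5 = 9/14.5 = 62%. This meets PR and fails VGPR.
- Ratio: 6/0.5 = 12, against a reference range of 0.26-1.65.
- With negative serum and urine immunofixation, no plasmacytoma, at most 5% marrow plasma cells and negative flow, every written condition for CR and MRD(-) CR is met.

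A second case goes further. A change from 40/1 to 25/1 mg/dL is a fall of (39 − 24)/39 = 38.5%, which is not even PR by FLC. The same negative tests would still give MRD(-) CR.

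**4. Effect on the primary rate.** Each affected patient contributes 1/50 = 2.0 points. The number affected (k) is an assumption, because the documents do not give it.

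| k | from 70% (half-width) | from 85% (half-width) |
|---|---|---|
| 0 | 70% (±12.7) | 85% (±9.9) |
| 1 | 68% (±12.9) | 83% (±10.4) |
| 3 | 64% (±13.3) | 79% (±11.3) |
| 5 | 60% (±13.6) | 75% (±12.0) |

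The half-widths describe sampling error only and do not allow for a one-directional shift in the definition.

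**The case against.** **The protocol does not ignore FLC.** Section 6.3.1 says the involved and uninvolved levels should be considered in assessing response, and it asks for two consecutive determinations where FLC is the main determinant. This stands, but it softens the gap without closing it. No threshold for CR is given, so two assessors could score the same patient differently and both comply.

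**Meeting both PR and MRD(-) CR is not a contradiction.** A reader might infer one, but response categories are nested, and a patient in CR normally also passes the PR threshold. The defect is narrower: the VGPR requirement on FLC is not carried up to the categories above it.

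**The combination may be rare.** This is the strongest point. An FLC-only patient has serum M-protein below 1 g/dL, so must qualify as SMM on at least 10% marrow plasma cells. Going from 10% to below 1 in 10^5 is about a 10,000-fold clearance (0.1/0.00001), beside only a 62% fall in the FLC difference. That is possible under the written rules, but nothing in the documents shows that it happened.

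**CR cannot be met before treatment.** A reader might infer that the serum and urine part is already satisfied at entry. It could be in some patients, but unmeasurable does not mean immunofixation-negative, and the marrow condition is not met at entry.

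**The omission may be partly deliberate.** Amendment L allowed patients without measurable disease because the endpoint had become MRD(-) CR. That explains a marrow-based endpoint. It does not explain directing FLC-only patients to FLC criteria and then giving none for CR. Whether the definition departs from the cited international criteria cannot be judged from these documents, and the point does not depend on it.

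**Conclusion.** The point holds as a defect in the endpoint rule for one subgroup. As written, an FLC-only patient whose FLC difference falls by less than 90% and whose ratio stays abnormal can count as a primary success, although the same patient fails VGPR by FLC.

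The effect could be an upward shift of 2 percentage points per affected patient at n=50. Its total is unknown and may be zero. It depends on how many FLC-only patients were enrolled and how many combined negative immunofixation, marrow and flow with an abnormal ratio; the documents give neither count. A reader might take the larger shifts in the table as an estimate of bias, or conclude that CR dates in the duration endpoints are wrong. The documents support neither: they show that the rule permits misclassification, not that it occurred.

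**What to change.** Add one sentence to the CR definition in Section 6.3.2.1, which then carries into MRD(-) CR. Limit it to patients whose sole measurable disease at baseline is serum FLC, meaning involved FLC of at least 10 mg/dL with an abnormal ratio and M-protein unmeasurable in serum and urine: *CR also requires a normal kappa/lambda ratio (0.26-1.65).* This respects the instruction in Section 6.3.1 that other patients are not judged on FLC.

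Do not add a general rule that no patient may be classed above VGPR without meeting VGPR. It would misclassify patients, admitted since Amendment L, with neither measurable M-protein nor measurable FLC. For example, take an M-spike of 0.8 g/dL with FLC going from 3.0/1.0 to 1.6/1.0 mg/dL. The ratio becomes normal (1.6), but the difference falls only from 2.0 to 0.6, or 70%, so the cap would bar this patient from the primary endpoint.

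Re-score the FLC-only patients from the values on file. Report the MRD(-) CR rate as the protocol now defines it and with the FLC condition, and give the number of FLC-only patients. If none is affected, say so.

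The cost is small. FLC is already scheduled at baseline, on day 1 of each induction cycle and every third cycle in extension (Section 3.3.7.3), so no new test is needed. There are two drawbacks. The reported rate may fall slightly. The re-score is also post hoc, since all participants had completed maintenance by February 2023 (Section 3.4, footnote g), and must be labelled so; this is why both rates should be shown.

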# • Near Complete Response (nCR)

Defined as absence of myeloma protein on electrophoresis, independent of immunofixation status[50]

# • Very Good Partial Response (VGPR)

Version Date: 01/01/2024

Serum and urine M-protein detectable by immunofixation but not on electrophoresis or 90% or greater reduction in serum M-protein plus urine M-protein level <100mg per 24h. If the serum and urine M-protein are unmeasurable, a ≥90% decrease in the difference between involved and uninvolved FLC levels is required in place of the M-protein criteria.

## • Partial Response (PR)

≥50% reduction of serum M-protein and reduction in 24-h urinary M-protein by ≥90% or to <200mg per 24h. If the serum and urine M-protein are unmeasurable, a ≥50% decrease in the difference between involved and uninvolved FLC levels is required in place of the M-protein criteria

# • Stable Disease (SD)

Not meeting criteria for CR, VGPR, PR or progressive disease. All categories also require no known evidence of progressive or new bone lesions if radiographic studies were performed. Radiographic studies are not required to satisfy these response requirements.

# Progressive disease (PD)

Requires any one or more of the following:

Increase of  $\geq$ 25% from lowest response value in the following on 2 consecutive measurements:

- Serum M-component and/or (the absolute increase must be  $\ge 0.5$ g/dl). The serum M-component increases of  $\ge 1$  gm/dl are sufficient to define relapse if starting M-component is  $\ge 5$ g/dl.
- $\circ$  Urine M-component and/or (the absolute increase must be  $\geq 200 \text{mg}/24 \text{h}$
- Only in patients without measurable serum and urine M-protein levels: the difference between involved and uninvolved FLC levels. The absolute increase must be >10mg/dl.
- o Bone marrow plasma cell percentage: the absolute % must be  $\ge 10\%$
- o Definite development of new bone lesions or soft tissue plasmacytomas or definite increase in size of existing bone lesions or soft tissue plasmacytomas
- o Development of hypercalcemia that can be attributed solely to the plasma cell proliferative disorder.

## • Relapse from CR

Any one or more of the following:

- Reappearance of serum or urine M-protein by immunofixation or electrophoresis. Appearance of monoclonal or oligoclonal bands that are different from original isotype may not be defined as "relapse from CR".
   Oftentimes, such bands may indicate fluctuations in immunological parameters that are not reflective of MM disease. In these situations, immunofixation and electrophoresis will be interpreted by the clinician before being labeled as "relapse".
- o Development of  $\geq 5\%$  plasma cells in the bone marrow

Version Date: 01/01/2024

o Appearance of any other sign of progression (i.e., new plasmacytoma, lytic bone lesion, hypercalcemia.

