## 6.3.4 Duration of Best Response

The duration of overall response is measured from the time measurement criteria are met for best response until the first date that recurrent or progressive disease is objectively documented.

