## 10.2 STATISTICAL ANALYSIS OF SECONDARY/EXPLORATORY ENDPOINTS

Secondary endpoints are duration of response and progression free survival (both biochemical progression and progression to overt symptomatic multiple myeloma). Duration of response is defined as time from response to disease progression or death. Progression free survival is defined as time of study entry to progression or death. Duration of response and progression free

*Version Date:* 01/01/2024

survival will be estimated using the Kaplan-Meier and log-rank methods. Secondary endpoints will also include rate and duration of MRD-negative CR and OS.

A number of correlative studies will be performed in order to assess carfilzomib in vitro biological activity and investigate minimal residual disease in SMM. Minimal residual disease will be further explored using multi-parametric flow cytometry, PCR-based techniques, and advanced imaging.

Beginning with Amendment L (version date 05/17/2018), the secondary objectives will also include:

- 1. To estimate the durable MRD (-) CR rate, estimating the fraction of patients who have an MRD (-) CR for 1 year as a minimum. This fraction will be estimated along with a 95% two-sided confidence interval.
- 2. To compare the outcomes among the 18 patients enrolled in 2014 or earlier to the 32 enrolled in 2017 or later because the diagnostic criteria for SMM vs. MM were revised in 2014 after the 18th patient was enrolled. The MRD (-) CR rates will be compared between these two cohorts of patients using a two-tailed Fisher's exact test. All other comparisons of outcomes between the two cohorts will be interpreted as exploratory and will be done using appropriate non-parametric statistical tests without adjustment for multiple comparisons.
- 3. To obtain and report safety data on all enrolled evaluable patients to fully characterize the safety of the regimen in a modestly large number of subjects treated on one protocol.

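### One unconfirmed reappearance of original-isotype M-protein ends duration of best response under 6.3.4 but not duration of response under 10.2

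*Combined protocol and SAP*

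**What the plan says.** Four rules in the combined protocol and SAP bear on this point.

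- **Entering response (6.3.1).** Confirmation of the M-protein or light-chain results "must be made by verification on two consecutive determinations".
- **Progressive disease (6.3.2.1).** The laboratory criteria need a rise of at least 25% "from lowest response value in the following on 2 consecutive measurements", each with an absolute minimum; for serum M-protein this is 0.5 g/dl.
- **Relapse from CR (6.3.2.1).** Any one listed item is enough. The first item is "Reappearance of serum or urine M-protein by immunofixation or electrophoresis". No size threshold and no repeat are stated. A band of another isotype is treated separately: "Appearance of monoclonal or oligoclonal bands that are different from original isotype may not be defined as" relapse from CR, and "In these situations, immunofixation and electrophoresis will be interpreted by the clinician before being labeled as" relapse.
- **Duration.** Section 6.3.4 runs duration "until the first date that recurrent or progressive disease is objectively documented". Section 10.2 says: "Duration of response is defined as time from response to disease progression or death".

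Sections 1.1.2 and 10.2 also list duration of MRD(-) CR and the rate of MRD(-) CR lasting at least one year. Neither states what ends an MRD(-) CR.

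**The concern.** The most sensitive M-protein event in the plan is the only one with no stated confirmation. A result that would not be enough to enter a response, and is far below what progression needs, is enough to leave CR. Where the duration clock stops at the first recurrence, transient positives accumulate with repeated testing. Duration is then pulled short, and patients tested more often have more chances to lose their response.

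Most patients are exposed. Section 10.1 reports that 17 of the first 18 had some form of CR and 16 were MRD(-). Duration of response and durable MRD(-) CR are named secondary objectives, so the event that ends them should be unambiguous.

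**Working it through.** No figure in the plan depends on this rule, so there is none to reproduce. The check is a comparison of the text, followed by an illustration.

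**Text: one patient under two definitions.** Take a patient in CR who has a faint original-isotype band on immunofixation at cycle 15, nothing on electrophoresis, and a negative result at cycle 18.

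- Under 6.3.2.1 and 6.3.4 this is relapse from CR, and duration ends at cycle 15.
- Under 10.2 the event is progression or death. The band meets no PD criterion: there is no 0.5 g/dl rise and no second consecutive measurement. Duration continues. The result even fits the VGPR description, which allows M-protein seen on immunofixation but not on electrophoresis.
- For MRD(-) CR, the definition is CR plus negative flow, and CR requires negative immunofixation. One positive result plausibly ends it, but no section says so.

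The two duration definitions also differ at the start (best response against response) and on death, which only 10.2 counts.

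**Illustration: inputs.**

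- Number of assessments: Section 6.3 schedules cycles 9, 12, 15, 18, 21, 24, 27, 30 and the end of 32, which makes 9. Four assessments at every third 28-day cycle span 4 × 84 = 336 days, about the one-year horizon of the durable rate.
- Transient-positive rate q per test for an original-isotype band: not in the documents. Assumed 0.5% to 5%, independent between tests, with each assessment counted as one test.

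**Formulas.**

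- Single-result rule: P = 1 - (1 - q)^k.
- Two-consecutive rule: start with a = 1, b = 0, hit = 0. At each test add b·q to hit, then replace a by (a + b)(1 - q) and b by (old a)·q. Here b is the probability that the last test was an isolated positive with no run of two so far.

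**Worked case, q = 5%, k = 4.** Single result: 1 - 0.95^4 = 0.1855. Two consecutive: hit is 0 after test 1, 0.0025 after test 2, 0.0025 + 0.0475 × 0.05 = 0.004875 after test 3, and 0.004875 + 0.0475 × 0.05 = 0.00725 after test 4.

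| Tests | Rule | q = 0.5% | q = 1% | q = 2% | q = 5% |
|---|---|---|---|---|---|
| 4 | single result | 1.99% | 3.94% | 7.76% | 18.55% |
| 4 | two consecutive | 0.007% | 0.03% | 0.118% | 0.725% |
| 9 | single result | 4.41% | 8.65% | 16.63% | 36.98% |
| 9 | two consecutive | 0.02% | 0.079% | 0.314% | 1.904% |

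Nine is an upper bound for serum immunofixation on the cycle 9-32 schedule. Section 3.3.7.3 and Study Calendar footnote f restrict it after baseline to patients in whom it is clinically indicated. Serum electrophoresis remains scheduled every third cycle. Urine electrophoresis and immunofixation are scheduled in 3.3.7.4 and footnote l but limited by footnote f.

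**The case against.** The strongest reply is that Section 10.2 is the statistical section and does not count relapse from CR at all. If 10.2 governs, a single band ends nothing. That is correct. A reader might infer from 6.3.4 alone that one transient band ends duration of response in this trial, and the documents do not support that without qualification. But both sections are current text and neither is given precedence. They cannot easily be read as two separate endpoints either: 6.3.4 is headed as duration of best response, yet its text describes duration of overall response. The conflict is therefore part of the point.

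Second, the only non-disease bands that the documents describe are those of a different isotype, and these are already set aside for clinician interpretation. That stands. The gap is confined to bands of the original isotype.

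Third, the relapse rule is silent on repeat testing; it does not say that one result suffices, and 6.3.4 asks for objective documentation. Fair, but an analyst applying the words has no basis for requiring two. The confirmation rule in 6.3.1 is limited to classifying a response.

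Fourth, the rates and their independence are assumptions, and the number of immunofixations is not fixed. This also stands. A reader might take the upper figures in the table as an estimate of bias in this trial; they are not. It also remains uncertain whether the two-measurement condition for PD reaches bone lesions and hypercalcemia, because the list layout is ambiguous. The comparison here uses only the laboratory increases.

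**Conclusion.** The point holds in a limited form. Under 6.3.2.1 and 6.3.4, one unconfirmed reappearance of original-isotype M-protein counts as relapse from CR and ends duration of best response, while entering response and laboratory PD each need two results. Section 10.2 gives a different end event, so the same patient can have two durations. Duration of MRD(-) CR and the one-year durable rate may be affected, because their end event is undefined.

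The direction of any bias under 6.3.4 is towards shorter duration. Its size cannot be found from the documents. The table shows only that, over the assumed range, a single-result rule is much more exposed to transient positives than a confirmed rule.

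A reader might extend this to the headline results. The text does not support that: the primary MRD(-) CR rate does not use the relapse rule, and PFS is defined by progression or death in both 6.3.3 and 10.2.

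**What to change.** For endpoint scoring only, with no change to treatment decisions:

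1. In the relapse-from-CR definition, require M-protein of the original isotype on two consecutive determinations, with relapse dated to the first. Keep single-event scoring for new bone lesions, plasmacytoma and hypercalcemia.
2. Reconcile 6.3.4 with 10.2: one start, one set of end events, and an explicit statement on whether relapse from CR is among them.
3. State what ends an MRD(-) CR, and apply the same confirmation rule to loss by M-protein.
4. Report duration under both the single-result and the confirmed rule. Study Calendar footnote g records that all participants had completed cycle 32 by February 2023. The change therefore comes after treatment is complete, and because the date stays at the first positive it can only lengthen duration or leave it as it is. Showing both rules lets the reader see what the change does.
5. In the sensitivity analysis, count as relapse an unconfirmed positive that is the last result, or one followed by death or new therapy.

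The cost is a few sentences and a second run of the duration analysis on results already collected. The downside is that some relapses will stay unconfirmed where no second result exists. This is a real possibility, since immunofixation was done only when indicated, and footnote q lets follow-up visits move to six months with a further six-month allowance. List these cases.
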